It is anticipated that fewer than 15% of entered subjects will be unevaluable at the 12 month follow-up visit due to loss to follow-up and/or missing primary angiographic occlusion or safety data. However, subjects with missing data at the time of endpoint analysis will have primary effectiveness and primary safety endpoint data imputed as last observation carried forward (LOCF). Subjects who receive the device but in whom there is no post-procedure data will be treated as failures for the primary effectiveness analysis; subjects who do not receive the device because of treatment failure due to reasons associated with the device will also be treated as failures. Subjects with no post-procedure endpoint data upon which to base a LOCF imputation will be excluded from the primary safety endpoint analyses; it is anticipated that fewer than 7% of MITT subjects will be excluded from either primary effectiveness or primary safety endpoint analyses. Thus, although the primary endpoint analyses will be in the Modified Intent to Treat (MITT) population for primary effectiveness and safety endpoints, up to 320 subjects will be enrolled to achieve approximately 300 subjects with post-procedure data in the MITT population. A group sequential design will be employed in which one primary endpoint interim analysis will be conducted after N=160 subjects have been enrolled and followed through 6 months post-procedure, to determine if the study should stop early for futility or tentative success; it is anticipated that there will be at least N=150 subjects with post-procedure data in the MITT population for this analysis. If the stopping rule is met for the trial to stop early for tentative success, a final confirmatory analysis will be conducted when all subjects have reached 12 months post-procedure. If the trial is not terminated early for futility or tentative success, then enrollment will continue up to the full enrollment sample size of N=320.

Patients who experience an AE of Special Interest and who have an MRS >2 at any clinical evaluation will be followed through 24 months post-procedure.

An independent core laboratory will perform the quantitative analysis for the primary and secondary effectiveness endpoints, as well as for subjects where the 12 month angiogram is an endpoint assessment. A medical monitor will adjudicate the relationship of AEs to the device, procedure, and/or underlying disease in accordance with the definitions specified within this protocol.

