## 9.5 Handling of Missing Data

Primary effectiveness and primary safety endpoint analyses will be conducted on the modified intent-to-treat (MITT) population, where subjects with missing data at the time of endpoint analysis will be imputed as last observation carried forward (LOCF); see Section 9.8 for analysis set definitions. Note that the immediate post-procedure evaluation will be utilized in this LOCF methodology if this is the last observation on file. MITT subjects who receive the device but in whom there is no post-procedure data will be treated as failures for the purpose of the primary effectiveness endpoint analysis; these subjects will be excluded from all other endpoint analyses. Subjects who do not receive the device because of treatment failure due to reasons associated with the device will also be treated as failures for the primary effectiveness endpoint analysis; these subjects will be excluded from all other endpoint analyses. MITT subjects who do not receive the device because of an intra-operative surgeon decision based on patient anatomy (e.g. vessel tortuosity) will be treated as missing (and not as failures) in all endpoint analyses, including the primary effectiveness and primary safety endpoint analysis.

All subjects who have died prior to an evaluation will have a mRS score of 6 imputed for that time point for analysis purposes.

All other analyses based upon MITT or PP population data will be based upon actual data, with no data imputation.

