10.1 General Conventions

According to the Close Out plan, only descriptive statistics and listings will be presented, no inferential statistics will be performed for the primary and secondary endpoint. Descriptive statistics for continuous variables will include the number of subjects, mean, standard deviation, median, minimum and maximum. Descriptive statistics for dichotomous/categorical variables will include the number and percentage of subjects. All summary tables will be presented overall. Unless specified otherwise, percentages are based on non-missing values, excluding missing data and subjects who early discontinued.

- Baseline

Baseline is defined as the last non-missing measurement prior to the index procedure.

- Study Day

Unless specified otherwise, Study Day will be calculated as the difference between the event date and the date of index procedure, i.e., event date - date of index procedure. The day of index procedure is considered as Day 0.

- Date conversion

For the purposes of statistical analyses, a month is considered equivalent to 30 days and a year is considered equivalent to 360 days.

- SAS version

All statistical analyses will be performed using SAS®, Version 9.2 or later, unless otherwise noted.

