10.4.1 Primary Endpoints

10.4.1.1 Primary Effectiveness Endpoint

- Rate of RACO at 12 months post-procedure according to the Raymond Scale as assessed by the Independent Core Laboratory.

The number and percentage of subjects with RACO at 12-Month Follow-up will be summarized based on the assessment from the Independent Core Laboratory.

- Subjects who are retreated (retreatment includes staged procedures) prior to 12 months angiographic imaging will be considered as not achieving complete aneurysm occlusion;
- Subjects who have missing values in Raymond Scale at 12-Month Follow-up will be excluded from analysis.

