10.6 Handling of Missing Data

Unless stated otherwise, missing data will not be imputed, percentages will be based on non-missing data.

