10.7 Sensitivity Analyses

Sensitivity analyses will not be performed for the final CSR.

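### SAP 10.4.1.1 makes the primary 12-month occlusion rate a complete-case rate still labelled mITT, and SAP 10.7 cancels every analysis that could show what the exclusion does

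*SAP*

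**What the plan says.** **Protocol.** Section 9.5 analyses the primary effectiveness endpoint in the MITT population, where "subjects with missing data at the time of endpoint analysis will be imputed as last observation carried forward (LOCF". The immediate post-procedure reading may serve as the last observation if nothing later exists. Two further groups stay in the denominator: "MITT subjects who receive the device but in whom there is no post-procedure data will be treated as failures", and "Subjects who do not receive the device because of treatment failure due to reasons associated with the device will also be treated as failures". Subjects not implanted because of an operator decision about anatomy are treated as missing. For planning, Section 3.1 states: "It is anticipated that fewer than 15% of entered subjects will be unevaluable at the 12 month follow-up visit".

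**SAP.** Section 10.4 keeps the primary effectiveness analysis in the mITT set, but 10.4.1.1 says: "Subjects who have missing values in Raymond Scale at 12-Month Follow-up will be excluded from analysis". The general rules agree with this. Under 10.1, "percentages are based on non-missing values, excluding missing data and subjects who early discontinued"; under 10.6, "missing data will not be imputed, percentages will be based on non-missing data". Retreatment before 12-month imaging still counts as not occluded. Section 10.7 adds: "Sensitivity analyses will not be performed for the final CSR". Sections 6 and 10.4 drop the hypothesis tests and keep 95% confidence intervals for description only.

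**The concern.** Early termination explains why the tests were dropped. The SAP gives no reason for also setting aside core-lab readings that are already held, and low enrolment does not prevent their use.

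Two kinds of subject leave the primary rate: those who died or were lost after an earlier reading, and those whom the protocol would have counted as failures. The SAP has a rule for retreatment before imaging but none for death. A subject retreated after rupture therefore counts as not occluded, while one who dies after rupture without a 12-month score leaves the denominator.

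With no test planned, the point estimate and its exact interval are what readers will take away. That interval covers sampling error among those with a 12-month score and says nothing about those without one. The mITT label suggests a fuller denominator than the rate has.

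**Working it through.** The documents give no figure for the effect of missing data, so there is none to reproduce. As a check on the reading of the endpoint and the 35% goal, the protocol's stated power of 87.7% at a true RCAO of 44% was recomputed. An exact two-stage calculation at 150 and 300 subjects, with two-sided 0.031 and futility not enforced, gives 87.6%.

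**1. The rules side by side**

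| MITT subject | Protocol 9.5 | SAP 10.4.1.1 |
|---|---|---|
| Lost or died after an earlier reading | Reading carried forward (no separate death rule for this endpoint) | Excluded |
| Device received, no post-procedure data | Failure | Excluded |
| No device, device-related reason | Failure | Excluded if no 12-month score |
| No device, anatomy | Missing | Excluded if no 12-month score |

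**2. Bounds on the all-subject rate**

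Inputs:
- m, the share without a 12-month score: 15%, the top of the planning expectation in Protocol 3.1. This is an assumption.
- p, the completers' rate: 44% (the protocol's planning rate), 50% (illustrative) and 58.2% (six-month rate in the sponsor's registry, Protocol 1.3.4).
- q, the occlusion rate among those excluded: unknown, between 0 and 1.

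All-subject rate = p(1−m) + qm. With q = 0 this is p(1−m), a shift of −mp. With q = 1 it is p(1−m) + m, a shift of +m(1−p).

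| p | Lower bound | Upper bound | Shift (points) |
|---|---|---|---|
| 44% | 0.44 × 0.85 = 37.4% | 37.4 + 15 = 52.4% | −6.6 / +8.4 |
| 50% | 0.50 × 0.85 = 42.5% | 42.5 + 15 = 57.5% | −7.5 / +7.5 |
| 58.2% | 0.582 × 0.85 = 49.47% | 49.47 + 15 = 64.47% | −8.7 / +6.3 |

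The interval is always m wide, here 15 points. At p = 50% the shift is ±3.5 points for m = 7%, ±5.0 for 10% and ±10.0 for 20%.

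**3. SAP rate against a carried-forward rate**

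Difference = p − [p(1−m) + qm] = m(p−q), where q is now the carried-forward rate among those excluded. At p = 50% and m = 15%:
- q = 58.2% (registry, six months): 0.15 × (0.50 − 0.582) = −1.23 points. The SAP rate is lower.
- q = 35% (the performance goal, as a low illustrative value): 0.15 × 0.15 = +2.25 points.
- q = 20.2% (registry, immediately post-procedure, relevant if only the acute reading exists): 0.15 × 0.298 = +4.47 points.

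**4. Protocol-defined failures**

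For these subjects q = 0, so leaving them out can only raise the rate. Their number is not in the documents.

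**The case against.** The case for leaving the SAP alone has substance.

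- The report is descriptive, with no success decision to alter.
- The omitted subjects are not lost to the report. Those with a six-month reading enter the six-month RCAO (SAP 10.4.2.1), deaths and discontinuations are tabulated with reasons (10.2), and death is part of a primary safety endpoint (10.4.1.2).
- Missingness should be limited. SAP 5.4 requires treated subjects to complete 12 months, and the 12-month window is widened to Day 270–450 from the protocol's 320–410.
- The 15% also covers missing safety data and subjects with no earlier reading, so it is wider than the group at issue.
- Carrying readings forward is not neutral. Registry occlusion rose from 20.2% immediately post-procedure to 58.2% at six months, so early readings may understate the 12-month rate.
- The Close Out Plan and table shells are separate documents. Missing counts by reason, or subject listings, may be planned there.

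All of this stands, and it limits the weight of the point. It does not remove it. The planned summaries are separate, and none ties a missing 12-month score to that subject's earlier reading. A reader with the mITT count could work out the crude bounds but could not rebuild the protocol's rate from these summaries.

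A reader might go further and infer that the exclusion favours the device. The documents do not show this: the bounds run both ways, and step 3 gives differences of either sign. A reader might also infer that death should count as failure in the headline rate. The protocol has no such rule. Under its own method, a subject who dies after a six-month score of 1 would count as occluded.

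**Conclusion.** The point holds as a gap in reporting. The SAP replaces the protocol's analysis with a complete-case rate, keeps the mITT label, and plans nothing that shows how far the primary estimate depends on who has a 12-month reading.

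At an assumed 15% missing, the all-subject rate could differ from the reported one by −6.6/+8.4 points at 44%, −7.5/+7.5 at 50% and −8.7/+6.3 at 58.2%. These are extremes that need every excluded subject to have the same outcome. The 15% is a planning figure for the full trial, and actual missingness in the terminated study is unknown. Against the protocol's rule the difference is probably smaller, and its sign is not established.

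Two inferences should be avoided. The 7.5 points at a 50% completers' rate is not a ceiling: it is 15% × 50%, and other rates give larger shifts. Nor does a bound falling below 35% change a trial conclusion, because the SAP makes no test against the goal.

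**What to change.** Keep the complete-case row in SAP 10.4.1.1 and label it as such. Beside it, report the number of mITT subjects without a 12-month score, by reason, with death shown separately. Add supportive rows over the mITT set:

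- **(a) The Protocol 9.5 rule:** last core-lab reading carried forward, with protocol-defined failures counted as failures. Subjects not implanted for anatomical reasons stay missing, as the protocol has it, and their number is stated.
- **(b) Bounds:** all missing scores, including deaths, counted as not occluded, with the all-occluded bound alongside.

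Amend 10.7 so that these rows are planned analyses. Do not redefine death as failure in the headline rate; row (b) shows its effect without a new endpoint definition.

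The cost is a change of SAP wording and a few table rows from data already held. Some supportive rates may be less favourable than the headline.

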10.4.1.2 Primary Safety Endpoints

- Incidence of major ipsilateral stroke and/or death

The incidence of major ipsilateral stroke and/or death will be evaluated from the start of the index procedure until the completion of the 12-Month Follow-up based on the assessment from DSMB adjudicated data.

The number and percentage of subjects with major ipsilateral stroke and/or death up to and including 12-Month Follow-up will be summarized.

- Incidence of In-sent stenosis

The number and percentage of subjects with in-stent stenosis up to and including 12 months post-procedure will be summarized based on the assessment from the Independent Core Laboratory. Subjects with missing data will be excluded from analysis.

10.4.2 Secondary Endpoints

All secondary endpoints will be summarized on mITT Analysis Set.

All angiographic imaging results will be based upon assessments by the independent Core Laboratory. A subject who is retreated (retreatment includes staged procedures) on or prior to the angiographic imaging assessment, is considered as a treatment failure for the evaluation of this endpoint. This applies to all secondary effective endpoints except the retreatment rate.

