### **3.2.3 Secondary Effectiveness Endpoints**

The following secondary effectiveness endpoints have been defined. Observed rates will be described for both the MITT and PP populations; All angiographic imaging results will be based upon assessments by the independent Core Laboratory. A subject who is retreated (retreatment includes staged procedures) is considered to be a treatment failure for endpoints based on angiographic imaging.

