## **4.0 ELIGIBILITY OF SUBJECTS, EXCLUSIONS AND REMOVAL OF SUBJECTS**

Subjects eligible for initial study screening are subjects who present with unruptured wide-neck, intracranial, saccular anterior circulation aneurysms and who are judged to be candidates for stenting. Every effort will be made to establish eligibility of the participants prior to enrollment.

Subjects who agree to voluntarily sign a study informed consent will be considered "enrolled" in the study, and will comprise the subject populations for this study.

Enrolled subjects who meet all of the general inclusion criteria and none of the general exclusion criteria described in this protocol will proceed with confirmation of angiographic inclusion/exclusion criteria.

Pre-treatment angiography performed during the index procedure will be utilized for final assessment of angiographic eligibility criteria. Subjects, who meet all of the general and angiographic inclusion/exclusion criteria, including the requirement for only one aneurysm to be treated, may be treated with ENTERPRISE. Subjects will be “entered” in the study (if the intent is to proceed with stent deployment) at the time of the start of the index procedure as defined in this protocol (see definitions). All subjects entered will be evaluated, regardless of sequence of treatment that ensues.

Subjects who are enrolled but not entered due to angiographic ineligibility resulting from either a pre-procedure angiogram or a pre-treatment angiogram will be considered an Angiographic Screening Failure (ASF) and will be followed for the period 72 hours following the end of the angiogram, or until discharge, whichever comes first, or to resolution of any adverse event, whichever is longer, and then will be discontinued from the study.

All subjects “entered” in the study are considered follow-up eligible and will be required to adhere to the follow-up schedule outlined in this protocol. Subjects who withdrew consent after treatment will be followed until the time of their withdrawal. Subjects who receive a retreatment of the study aneurysm will be followed for safety until the completion of their 24 month follow-up or premature study termination. These aneurysms will not be assessed for effectiveness beyond the retreatment.

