### **6.2.2 Index Procedure**

For the ENTERPRISE Device see accompanying IFU for complete instructions including warnings and precautions, on intracranial stent preparation and usage. The index procedure (pre-treatment, intra-procedure, and immediate post-treatment of the index), 6 month and 12 month follow-up, any unscheduled and any pre-retreatment angiograms must be performed according to the study Core Lab Manual. Per the study protocol, the stenting and coiling must both be performed during the index procedure, and the embolization coils must be placed after the stent is deployed. Staged procedures are not allowed under this study protocol. If it becomes medically necessary to stage the stenting and coiling procedures this will be considered a treatment failure.

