### **6.3.6 12 Month Follow-up (Clinic Visit & Angiogram)**

The 12 month follow-up must occur between 320 days and 410 days from the date of the index procedure.

All subjects entered into the study will be followed for adverse event assessment at 12 months.

The 12 month follow-up evaluations must be performed at the investigational site. All subjects entered into the study will be submitted to the following:

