10.4 Primary and Secondary Endpoint Analyses.....	10
10.4.1 Primary Endpoints	10
10.4.2 Secondary Endpoints	11
10.4.3 Ancillary Endpoint Analyses.....	13
10.4.4 Safety Follow-up through 24 months post-procedure	14
10.5 Plans for Interim Analysis	14
10.6 Handling of Missing Data	14
10.7 Sensitivity Analyses	14
10.8 Subgroup Analysis.....	14
10.9 Assessment of Site Homogeneity	14
10.10 Additional Endpoint Analyses.....	14
11. Appendix: Tables, Listings and Graphs Shells	15

1. Study Design

This is a prospective, multi-center, single arm, clinical study to evaluate the safety and effectiveness of the ENTERPRISE stent when used in conjunction with endovascular coil embolization in the treatment of unruptured wide-neck, intracranial, saccular anterior circulation aneurysms (≤ 10 mm) arising from a parent vessel with a diameter of ≥ 2.5 mm and ≤ 4 mm. Due to low enrollment in the study, the Sponsor has decided to terminate the study early. The details regarding the length of follow-up for ongoing subjects are documented in the Close Out Plan.

2. Treatment Assignment

This is a single arm study with no comparator device, eligible subjects are expected to be treated with any of the following study devices.

- ENTERPRISE® Vascular Reconstruction Device and Delivery System (ENTERPRISE VRD system),
- ENTERPRISE® 2 Vascular Reconstruction Device and Delivery System (ENTERPRISE 2 VRD system).

3. Randomization and Blinding Procedures

No randomization or blinding is applied in the study.

4. Interval Windows

The following analysis intervals will be applied on the study.

Table 1: Analysis Intervals for Assessments

Visit	Description	Analysis Interval
Screening/Baseline	Screening/Baseline	Day -14 – Day 0
Immediate Pre-Procedure	Immediate prior to treatment	Within 12 hours prior to procedure
Index Procedure	Treatment	Day 0
Immediate Post-Procedure	Immediate post treatment	Within 12 hours post-procedure
Hospital Discharge	Hospital discharge	12 hours to 36 hours post-procedure
30-Day Follow-up	Telephone interview	Day 10 – Day 60
6-Month Follow-up	Clinic visit & Angiogram	Day 92 – Day 240
12-Month Follow-up	Clinic visit & Angiogram	Day 270 – Day 450
18-Month Follow-up	Telephone interview	Day 457 – Day 592
24-Month Follow-up	Clinic visit & MRA or Angiogram	Day 685 – Day 775

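### The SAP can count a scan from Day 270 to Day 319 as a 12-month complete/partial occlusion success although the aneurysm was retreated after it and before the 12-month visit

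*SAP*

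**What the plan says.** - **Retreatment, secondary endpoints.** Protocol 3.2.3, like the Overview, sets no time limit: "A subject who is retreated (retreatment includes staged procedures) is considered to be a treatment failure for endpoints based on angiographic imaging". SAP 10.4.2 adds one tied to the image: "A subject who is retreated (retreatment includes staged procedures) on or prior to the angiographic imaging assessment, is considered as a treatment failure". On scope it says: "This applies to all secondary effective endpoints except the retreatment rate".
- **Retreatment, primary endpoint.** Protocol 3.2.1 fails a subject retreated before the 12-month visit. SAP 10.4.1.1 again refers to the image: "Subjects who are retreated (retreatment includes staged procedures) prior to 12 months angiographic imaging will be considered as not achieving complete aneurysm occlusion".
- **12-month window.** Protocol 6.3.6: "The 12 month follow-up must occur between 320 days and 410 days from the date of the index procedure". SAP 4, Table 1: "Day 270 – Day 450". If a window holds several measurements, SAP 4 takes the most recent. It does not exclude unscheduled or pre-retreatment scans.
- **Definitions.** Protocol Appendix 1 defines complete/partial occlusion with the condition that the aneurysm had no further treatment after the index procedure. For percent occlusion it keeps subjects retreated before the visit in the analysis, under a separate Retreated category. SAP 5.2.1 has neither of these. It does keep the no-further-treatment condition for procedure success, and SAP 5.1.1 keeps it for primary RCAO.
- **Scans around a retreatment.** Protocol 6.2.2: "any unscheduled and any pre-retreatment angiograms must be performed according to the study Core Lab Manual". Protocol Table 1 (footnote on unscheduled angiograms) sends unscheduled scans to the core laboratory. For retreated aneurysms Protocol 4.0 says: "These aneurysms will not be assessed for effectiveness beyond the retreatment".

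**The concern.** A retreatment usually follows the angiogram that prompted it. If failure requires retreatment on or before the scan that is used, and that scan may be the prompting one, the rule misses the cases it was meant to catch. The earlier opening of the window makes this more likely, because a scan taken well before the 12-month visit can now fill the 12-month slot.

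The endpoint at stake is 12-month complete/partial occlusion, where Raymond 2 counts as success. An aneurysm that needed more treatment before 12 months could be reported as adequately occluded at 12 months. Under SAP 10.4.2 the retreatment failures are a subset of those under Protocol 3.2.3, so the departure can only raise the success rates. SAP 10.1 confines the analysis to descriptive statistics, so these rates are the study's result on these endpoints.

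**Working it through.** The plan states no figure on this point, so there is none to reproduce. The check has three steps.

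**1. Windows.** SAP: 450 − 270 + 1 = 181 days. Protocol: 410 − 320 + 1 = 91 days. The SAP window opens 320 − 270 = 50 days earlier (Day 270 to Day 319) and closes 450 − 410 = 40 days later.

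**2. The literal rules applied to constructed records.** SAP: take the latest scan in Day 270–450, apply the retreatment rule, then the score. Protocol 3.2.3: any retreated subject fails.

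| Scan(s) | Retreated | SAP, complete/partial | SAP 10.4.1.1, primary | Protocol 3.2.3 |
|---|---|---|---|---|
| Raymond 2, Day 285 only | Day 300 | **success** | failure by score | failure |
| Raymond 2, Day 285; Day 365 scan also read | Day 300 | failure | failure | failure |
| Raymond 3, Day 285 only | Day 300 | failure by score | failure by score | failure |
| Raymond 1, Day 285 only | Day 300 | **success** | **success** | failure |
| Raymond 2, Day 285 only | Day 285 | failure | failure by score | failure |
| Raymond 2, Day 250 only | Day 275 | excluded as missing | excluded as missing | failure |

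Row 1 is the case at issue. Row 2 shows that it needs the absence of a later in-window reading. Row 4 is the only route to the primary endpoint: the core laboratory must read the last scan before retreatment as complete obliteration. Row 6 is a neighbouring gap: a retreated subject with no in-window scan may drop out of the denominator.

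**3. Size.** One subject moves a rate by 1/n. The final n is not in the documents. For assumed n of 30, 50, 100 and 150, this is 3.3, 2.0, 1.0 and 0.7 percentage points.

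For an expected size, assume (none of this is in the documents) that 5–10% of subjects are retreated, evenly over 365 days, that 30–60% of them are Raymond 2 on the scan before retreatment, and that retreatment follows that scan closely.

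Inflation = share retreated × share Raymond 2 × 50/365

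- Low: 0.05 × 0.30 × 50/365 = 0.0021, or 0.2 points.
- High: 0.10 × 0.60 × 50/365 = 0.0082, or 0.8 points.

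This is an upper bound under these assumptions, because it supposes that no such subject has a later reading. At n = 100 it amounts to 0.2 to 0.8 of a subject, so most likely none or one.

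**The case against.** **A time limit is needed.** Read literally, the untimed protocol rule would fail a subject's acute result because of a retreatment in month 11. This stands. The fault is that the SAP ties the limit to the image. Protocol 3.2.1 and the percent occlusion definition in Appendix 1 already tie it to the visit.

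**A later scan normally exists.** Protocol 6.3.6 schedules a 12-month angiogram for every entered subject, and the SAP uses the most recent reading. If nothing after retreatment were ever read, the SAP's own rule could hardly operate. This stands in part: exposure is limited to retreated subjects without a later in-window reading. Protocol 4.0 makes such subjects plausible, and the SAP does not say whether their later scans are used.

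**Using a pre-retreatment scan as the visit image is an inference.** The protocol lists such scans apart from the 6- and 12-month ones, and the SAP does not say that they fill a visit slot. That is correct, but the SAP windows go by day alone and exclude nothing.

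**Stronger readings that the documents do not support:**

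- *RCAO is inflated.* Raymond 2 or 3 already fails by score, which leaves only row 4.
- *Procedure success is wrong in the same way.* SAP 5.2.1 keeps the no-further-treatment condition there, so the SAP is ambiguous rather than plainly wrong.
- *The 90–99% occlusion category is a false success.* Percent occlusion is a distribution with no success threshold. What is missing is the Retreated category.
- *The 6-month rate is inflated too.* Day 92 is the protocol's own lower bound, and the SAP moved only the upper one (212 to 240). A scan from Day 92 can be a valid 6-month image.
- *All of Day 270 to Day 365 counts.* That would give 95/365, or 0.4 to 1.6 points, but from Day 320 a scan can be a valid protocol 12-month image.

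**Conclusion.** The point holds for 12-month complete/partial occlusion. A subject with a Raymond 2 scan in Day 270–319, retreated after it but before the 12-month visit and with no later in-window reading, is a success under the SAP and a failure under the protocol. The direction always favours the device.

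The size is 1/n per subject, and at most about 0.2 to 0.8 points under the assumed retreatment frequency, timing and Raymond 2 share. No test or error rate is affected: SAP 6 drops the hypothesis tests and says that the confidence intervals are not for inference. The retreatment rate is also reported separately, so these subjects do not disappear from the report. The point is a small, one-directional bias that is easy to remove before analysis. It does not threaten the primary result.

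**What to change.** In SAP 10.4.1.1 and 10.4.2:

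1. Count any retreatment before the 12-month follow-up visit as failure for the 12-month angiographic endpoints, whatever scan falls in the window. If no such visit takes place, use nominal Day 365 as the cut-off. This also settles the retreated subject with no in-window scan.
2. For a retreated subject, do not use an unscheduled or pre-retreatment scan taken before Day 320 as the 12-month image. A scheduled 12-month angiogram inside the protocol window that itself prompts retreatment stays a valid visit image. A ban on every pre-retreatment scan would discard it wrongly.
3. In SAP 5.2.1, restore the no-further-treatment condition for complete/partial occlusion and add the Retreated category to percent occlusion, both from Protocol Appendix 1.
4. State that the condition in the procedure success definition is applied by the same visit-based cut-off.

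The cost is SAP wording and minor programming. The affected rates become slightly less favourable.
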